11.2 Analysis of the Secondary Efficacy Endpoints

The Efficacy Population with LOCF will be used for secondary endpoint analyses. All secondary endpoints will be presented in patient listings by visit and eye where appropriate, however, summary tables will be created for CAS only.

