9.2.3.1. Efficacy Analysis for the Randomized Treatment Arms

The primary clinical endpoint analysis is the percentage of patients in the randomized treatment arms who have received LASN01 (pooled analysis of 300 and 600 mg Q4W) showing a response in proptosis (≥ 2 mm decrease from Baseline) in the study eye without deterioration (≥ 2 mm increase) of proptosis in the fellow eye at Week 37 compared with placebo.

The primary endpoint will be analyzed using a one-tailed Fisher’s exact test at an alpha of 0.10 and will report the percentage of LASN01 (300 mg and 600 mg Q4W pooled) responders compared to placebo responders at the Week 37 timepoint. Results, including p-values, will be summarized and presented in contingency table. 95% confidence intervals will be reported.

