9.5. Sample Size Determination

This study will enroll up to 36 evaluable patients with TED in 4 treatment arms. Approximately 24 patients will be randomized to LASN01 600 mg Q4W, LASN01 300 mg Q4W, or placebo treatment arms in a 1:1:1 ratio [REDACTED].

For the three randomized treatment arms: The pooled primary analysis represents an aggregate 2:1 randomization of LASN01:placebo with approximately 24 total patients. The success rate for placebo was assumed to be 15% ([Teprotumumab – FDA Summary Basis of Approval 2020](#)). Assuming a pooled success rate for LASN01 of 65% (ie, a pooled absolute treatment effect of 50% relative to placebo), the proposed sample size of 8 patients per treatment group gives approximately 81% power at the 10% level of statistical significance for a 1-sided Fisher’s exact test of superiority of LASN01. If the placebo rate is 10% instead, the proposed sample size gives approximately 90% power at the 10% level of statistical significance. All calculations were performed using [R Core Team \(2022\)](#) Version 4.2.1. Power was determined using simulation methods with a simulation size of 10,000 and simulations were implemented using the ‘statmod’ package ([Giner 2016](#)).

[REDACTED]

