2. Study Objectives and Endpoints

Objectives	Corresponding Endpoints
Primary: Efficacy	
To assess changes in proptosis following IV administration of 2 dose levels of LASN01 in patients with TED	
For randomized treatment arms:
 
 Percentage of patients who have received LASN01 (pooled analysis of 300 and 600 mg every four weeks [Q4W]) showing a response in proptosis (≥ 2 mm decrease from Baseline) in the study eye and separately in either eye without deterioration (≥ 2 mm increase) of proptosis in the fellow eye at Week 37 following treatment with IV LASN01 compared with placebo

CONFIDENTIAL

The contents of this document are confidential to [REDACTED]
Unauthorized use, disclosure, or reproduction is strictly prohibited.

Secondary: Efficacy	
To assess changes in TED-related clinical parameters following IV administration of LASN01 in patients with TED	
For randomized treatment arms:
 
 Percentage of patients who have received LASN01 (600 mg Q4W) showing a response in proptosis (≥ 2 mm decrease from Baseline) in either eye without deterioration (≥ 2 mm increase) of proptosis in the other eye at Weeks 17, 21, 25, 29, 33, 37, 41, 45, 49, 53, 57, 65, and 73 following treatment with IV LASN01 compared with placebo Percentage of patients who have received LASN01 (300 mg Q4W) showing a response in proptosis (≥ 2 mm decrease from Baseline) in either eye without deterioration (≥ 2 mm increase) of proptosis in the other eye at Weeks 17, 21, 25, 29, 33, 37, 41, 45, 49, 53, 57, 65, and 73 following treatment with IV LASN01 compared with placebo Percentage of patients who have received LASN01 (pooled analysis of 300 and 600 mg Q4W) showing a response in proptosis (≥ 2 mm decrease from Baseline) in either eye without deterioration (≥ 2 mm increase) of proptosis in the other eye at Weeks 17, 21, 25, 29, 33, 41, 45, 49, 53, 57, 65, and 73 following treatment with IV LASN01 compared with placebo Mean change from Baseline in proptosis in patients who have received LASN01 (600 mg or 300 mg Q4W) compared with placebo at Weeks 17, 21, 25, 29, 33, 37, 41, 45, 49, 53, 57, 65, and 73 Changes in TED-related clinical parameters (CAS) across both LASN01 treatment arms (pooled analysis of 300 and 600 mg Q4W) and in each individual LASN01 treatment arm (600 mg or 300 mg Q4W) compared with placebo at Weeks 17, 21, 25, 29, 33, 37, 41, 45, 49, 53, 57, 65, and 73
Primary: Safety	

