2.2 Statistical Hypotheses

The primary clinical endpoint will be assessed using a one-sided Fisher's exact test at a 0.10 significance level. This analysis combines the 600 mg and 300 mg Q4W treatment arms ("pooled group") and compares them to placebo.

- Null Hypothesis (H_0): At Week 37, the percentage of patients showing a proptosis response in the study eye without deterioration in the fellow eye and separately in either eye is less than or equal in the LASN01 pooled group (300 mg and 600 mg) compared to placebo.
- Alternative Hypothesis (H_1): At Week 37, this percentage is greater in the LASN01 pooled group compared to placebo.

3. Study Design and Procedures

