11.1 Analysis of Primary Efficacy Endpoint(s)

The primary efficacy endpoint is the percent of patients showing a response in proptosis measured using Hertel exophthalmometer (≥ 2 mm decrease from baseline) in the study eye and separately in either eye without increased proptosis (≥ 2 mm increase) in the other eye at Week 37 (Day 253) as measured by Hertel Exophthalmometer. The primary efficacy endpoint will be assessed with a one-sided Fisher's exact p-value comparing the pooled active group to placebo at each visit, including the primary endpoint visit at Week 37. Interpretation of statistical significance should be made at the $\alpha=0.1$ level. Two-sided 95% CIs for responder analyses may be calculated with the Clopper-Pearson exact method.

Fisher's exact test syntax:

```
Proc sort data = <data>;
    by TRTPN descending AVALC; *orders the responses;
run;

proc freq data=<data> order=data; *Keeps the order in the dataset;
    tables TRTPN*AVALC / fisher;
run;

where TRTPN is planned treatment (1=Active and 2=Placebo)
```

CONFIDENTIAL

The contents of this document are confidential to [REDACTED]
Unauthorized use, disclosure, or reproduction is strictly prohibited.

AVALC is the responder variable (Y = response in proptosis of ≥ 2 mm decrease from baseline in the study eye and separately in either eye and < 2 mm increase in the other eye; and N = response of < 2 mm decrease from baseline in the study eye and separately in either eye or ≥ 2 mm increase in the other eye).

Note: with the above ordering, the right-sided p-value will be the correct one-sided p-value from Fisher's exact test for the primary hypothesis.

The primary efficacy analysis will utilize the Efficacy Population with LOCF. Additional sensitivity analysis may be conducted on the primary efficacy endpoint with observed data only (ODO) using study eye.

The percentage of proptosis responders by treatment arm (pooled active group and placebo) over time through Week 37 using line graphs for the Efficacy Population with LOCF will be produced for study eye and either eye separately.

Tables and figures will be provided for the individual treatment groups and pooled active group for all available visits while Week 37 remains the primary endpoint.

. A listing of proptosis in both eyes will be provided.

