Due to several consent withdrawals and patients declining to re-consent for the 12-month extension, the Sponsor unmasked the clinical team to assess whether early study termination was appropriate. Investigators, the CRO clinical operations team, and CRO statisticians remained masked until the database lock. The following specific changes have been made and the additions are considered exploratory:

- Due to early termination of the study, only proptosis measured by Hertel and Total CAS will be analyzed in tables. Other secondary and exploratory endpoints will be listed.
- Either eye responder analyses have been added for proptosis by Hertel and Total CAS, and either eye continuous analyses have been added for Total CAS. Either eye responder and continuous Total CAS analyses will identify an eye at Week 37 (Day 253) and use that same eye in the analysis for each visit.
- A sensitivity analysis, as defined in protocol Section 9.2.4, has been added for Total CAS in the study eye and separately for either eye. Only the pooled active group will be compared to placebo. The sensitivity analysis of the primary responder rate for proptosis from protocol Section 9.4.2. has been removed.

CONFIDENTIAL

The contents of this document are confidential to [REDACTED]
Unauthorized use, disclosure, or reproduction is strictly prohibited.

- An ANCOVA model has been added to existing mean and mean change from baseline Total CAS tables. The model includes baseline and treatment as factors and will be run separately for each eye (study eye and either eye) and visit. Only the pooled active group will be compared to placebo.
- 95% CI for proptosis responder analysis has been removed
- LOCF has been added as the imputation method for missing data for all efficacy analyses.
- Per Protocol Population analyses have been removed.
- ODO analyses have been added for all proptosis and CAS tables to check robustness of results.

17. References

1. Giner G, Smyth GK (2016). statmod: probability calculations for the inverse Gaussian distribution. R Journal 8(1), 339-351.
2. ICH Harmonised Tripartite Guideline: Statistical Principles for Clinical Trials E9. International Council for Harmonisation of Technical Requirements for Pharmaceuticals for Human Use. 05 February 1998.

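### Change in Hertel proptosis is still a listed secondary endpoint but has no analysis, and the SAP gives no settled interval for the responder-rate difference

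*SAP*

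**What the plan says.** **Continuous proptosis.** Protocol Section 9.2.4 lists mean change from baseline in proptosis as a secondary analysis, with one bullet for 600 mg and one for 300 mg, each against placebo. It gives no pooled version. SAP Section 2 keeps the endpoint: "Mean change from Baseline in proptosis in patients who have received LASN01 (600 mg or 300 mg Q4W) compared with placebo". SAP Section 1 then restricts summaries to the proptosis responder and Total CAS because of early termination. Section 11.2 says "All secondary endpoints will be presented in patient listings by visit and eye where appropriate, however, summary tables will be created for CAS only". Section 11.1 gives the proptosis readings a listing. Section 16 uses broader words: proptosis by Hertel and Total CAS are both to be analysed in tables, with no limit to responders.

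**Total CAS, for comparison.** Section 11.2.1 gives it descriptive statistics, one-sample and two-sample t-tests, an optional CI for the difference, ANCOVA and MMRM. Section 16 removes the protocol's MMRM sensitivity analysis for proptosis and adds one for Total CAS.

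**Intervals for responders.** Protocol Section 9.2.3.1, on the primary endpoint, states "95% confidence intervals will be reported". SAP Section 16 states "95% CI for proptosis responder analysis has been removed". SAP Section 11.1 states that two-sided 95% "CIs for responder analyses may be calculated with the Clopper-Pearson exact method". SAP Section 6.3 makes two-sided 95% the default for differences between arms and names no method. The test is fixed in SAP Section 2.2: "The primary clinical endpoint will be assessed using a one-sided Fisher's exact test at a 0.10 significance level".

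**The concern.** SAP Section 1 calls the study signal-seeking, and it has about 24 randomised patients. What a reader most needs from it is the size of the effect on the primary measure and its uncertainty. As written, proptosis is tested only as a yes/no outcome, and the difference in rates may be reported without an interval. A non-significant Fisher test reported that way cannot separate little effect from too few patients. Meanwhile a secondary measure, Total CAS, receives the full set of estimates.

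Early termination is the stated reason for the cut, but it does not explain this pattern. The Hertel readings in mm are needed anyway to derive the responder, and new CAS models were added at the same time. Section 16 also reports that the sponsor unmasked its clinical team, so dropping a protocol-specified analysis of the primary measure needs a justification that the SAP does not give. Finally, a programmer working from Sections 6.3, 11.1 and 16 cannot tell which interval to produce, or whether to produce one.

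**Working it through.** **Inputs.** Protocol Section 9.5: placebo response 15% (alternative 10%), pooled LASN01 response 65%, 16 v 8 patients. SAP Section 2.2: one-sided Fisher's exact test at 0.10. The documents give no SD for change in proptosis.

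**1. The plan's power figure.** Sum the binomial probabilities of every outcome (x of 16, y of 8) whose one-sided Fisher p is at most 0.10.
- 65% v 15%: 81.8% (plan: about 81%).
- 65% v 10%: 89.7% (plan: about 90%).

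Both reproduce.

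**2. Power for mean change, same patients and rates.** Assume normal changes with equal SD and ignore the fellow-eye condition. The responder rates then fix the standardised difference:

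d = z(0.65) − z(0.15) = 0.385 + 1.036 = 1.42

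For a one-sided t-test at 0.10, the noncentrality is d / √(1/n₁ + 1/n₂).
- Pooled, 16 v 8: 1.42 / √(1/16 + 1/8) = 3.28 on 22 df.
- Per dose, 8 v 8: 1.42 / √(1/8 + 1/8) = 2.84 on 14 df.

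| Comparison | Fisher | t-test on change |
|---|---|---|
| Pooled, 65% v 15% | 81.8% | 97.4% |
| Pooled, 65% v 10% (d = 1.67) | 89.7% | 99.4% |
| Pooled, 45% v 15% (d = 0.91) | 41.8% | 78.3% |
| Per dose, 8 v 8, 65% v 15% | 65.4% | 93.0% |
| 12 v 6, 65% v 15% | 63% | 93% |
| 8 v 4, 65% v 15% | 43% | 83% |

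The per-dose Fisher figure counts p exactly equal to 0.10 as significant; otherwise it is 63%. The last two rows show smaller numbers, which matter in a study that stopped early. Rounding readings to 0.5 or 1 mm, with an assumed SD of 1.5 to 2.5 mm, leaves pooled t-test power at about 97%.

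**3. Which interval each section would give.** Take 10/16 v 1/8, near the planned rates.
- Clopper-Pearson (Section 11.1): 35% to 85% on LASN01 and 0.3% to 53% on placebo. These are two single-arm intervals.
- Newcombe interval for the difference of 50 points: 8 to 72 points at 95%.

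Section 11.1's method yields the first pair and not the second. Section 6.3 would call for the second but names no method. Section 16 would give neither.

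**4. Interval against test.**
- 8/16 v 1/8: Fisher p = 0.087, positive under the plan. The 95% Newcombe interval is −3 to 62 points; the 80% interval is 11 to 55.
- 7/16 v 1/8: Fisher p = 0.142, negative. The 80% Newcombe lower limit is about +5 points.

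So neither level always agrees with the Fisher test.

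**The case against.** A reader might infer more from these sections than they support, and the other side is right on several counts.

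- **That the primary measure is left with no effect estimate.** Section 11.1 keeps responder tables and figures for each dose and the pooled group at all visits, so a point difference can be read off. What is missing is a specified interval for that difference, and any effect in mm.
- **That the confidence interval is simply gone.** Section 16 says so, but Section 11.1 still allows one and Section 6.3 sets a default for differences. The documents show a contradiction, not a clean removal.
- **That no continuous proptosis table will exist.** Section 16's wording on tables is broad enough to cover one. Sections 1 and 11.2 point the other way. The SAP's table list (Section 18) was not in the text available, so the final outputs could not be checked.
- **That everything restored would be pre-specified.** Only the per-dose mean change clearly is. Protocol Section 9.2.4's MMRM compares LASN01 with placebo, but it is headed as a sensitivity analysis of the binary primary endpoint and names no continuous outcome. After the sponsor's unmasking, a pooled contrast in mm cannot be presented as planned.
- **That a 95% interval is wrong beside a one-sided 0.10 test.** It is a declared descriptive convention and need not invert the test. Moving to 80% only creates the opposite disagreement, as step 4 shows.

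It is also fair that the narrowing is disclosed, that individual readings are still listed, and that this is proof-of-concept work. The gap survives all of this: a listed endpoint has no method, and the interval statements conflict.

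**Conclusion.** The point holds. A protocol-specified endpoint on the primary measure stays in SAP Section 2 but is reduced to a listing by Sections 1, 11.1 and 11.2. The interval that the protocol promised is removed in one section, optional in another by a single-arm method, and covered in a third by a default without a method.

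The loss of power is about 15 percentage points pooled (97.4 − 81.8 = 15.6) and 28 per dose (93.0 − 65.4 = 27.6) at the plan's own rates, and larger for pooled effects below the planned one. These figures assume normal changes, equal SD and complete data, and they ignore the fellow-eye condition. They are for a t-test, not for a particular adjusted model. They show that continuous analysis is likely to be much more informative; they do not establish it as the most powerful analysis possible. With the study already terminated, the stronger argument is estimation: an effect in mm and an interval for the rate difference. This should be corrected, but it does not invalidate the primary test.

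**What to change.** 1. Add to SAP Section 11 a table of change from baseline in study-eye Hertel proptosis, with a baseline-adjusted difference in mm and 95% CI at Week 37. Show each dose against placebo as the pre-specified comparison. Show the pooled contrast as well, labelled supportive or post hoc because the sponsor's clinical team was unmasked.
2. Report the responder-rate difference with a 95% interval from a named method for a difference, for example exact unconditional or Newcombe. State that it is descriptive and need not agree with the one-sided 0.10 Fisher test.
3. Delete the Section 16 bullet that removes the interval, and reconcile Sections 1, 2, 6.3, 11.1, 11.2 and 16. Correct Section 16's reference to protocol Section 9.4.2; the MMRM is in protocol Section 9.2.4.

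The cost is two or three extra tables from data already collected for the primary endpoint. No new data and no change to the primary test are needed.

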11.2.1 CLINICAL ACTIVITY SCORE

The CAS measures the presence (scored as 1) or absence (scored as 0) of the following signs and symptoms:

- Spontaneous orbital pain
- Gaze-evoked orbital pain
- Eyelid swelling due to active TED
- Eyelid erythema
- Conjunctival redness due to active TED
- Chemosis
- Inflammation of the caruncle or plica

CONFIDENTIAL

The contents of this document are confidential to [REDACTED]
Unauthorized use, disclosure, or reproduction is strictly prohibited.

Total CAS is the sum of these scores and is measured at the appropriate visits according to the schedule of assessments. A CAS responder is defined as patients achieving a Total CAS score of 0 or 1 at a post-baseline visit. A CAS Responder must have at least a score of 2 at baseline to be included in analyses. Study eye and either eye responder analyses will use a one-sided Fisher's exact p-value to compare the individual treatment arms and pooled active group to placebo at each visit.

Two-sided 95% CIs for responder analyses may be calculated with the Clopper-Pearson exact method.

Total CAS and its change from baseline results will be summarized for each visit with descriptive statistics for each individual arm and the pooled active group. P-values for the one-sample t-tests will be provided to assess each individual arm and the pooled treatment arm change from baseline. The 95% CIs may also be constructed around the treatment difference, and p-values from a two-sample t-test will be provided to assess the individual treatment arm and the pooled active treatment differences as compared to placebo. An analysis of covariance (ANCOVA) model with baseline and treatment group as fixed factors will be used to compare pooled active group to placebo for study eyes and separately for either eyes at each visit.

A restricted maximum likelihood-based mixed model repeated measures (MMRM) analysis of the longitudinal observations at each post-baseline visit will be used to model change from baseline in Total CAS in the study eye only. The model will include the categorical effects of treatment (pooled 300 mg and 600 mg, and placebo), visit (visits through Week 37), and the continuous covariate of baseline proptosis as fixed factors, and within-patient errors will be modeled using the repeated statement. An unstructured-covariance matrix will be used to model the within-patient error. If the fit of the unstructured covariance structure fails to converge, the following covariance structures will be tried in this order until convergence is reached: toeplitz with heterogeneity, autoregressive with heterogeneity, toeplitz, and autoregressive. The Kenward-Roger method will be used to determine denominator degrees of freedom. The overall least squares (LS) means and corresponding SEs, 95% CIs, and p-values (only for treatment comparisons) for pooled active group, and for the treatment difference compared to placebo may be presented through Week 37.

MMRM syntax:

```
proc mixed data=<data>;
  class AVISITN TRTPG1 SUBJID;
  model CHG = BASE AVISITN TRTPG1 /ddfm=KR;
  repeated / subject=SUBJID type=UN;
```

CONFIDENTIAL

The contents of this document are confidential to [REDACTED]
Unauthorized use, disclosure, or reproduction is strictly prohibited.

```
lsmeans TRTPG1 / cl pdiff;
ods output lsmeans=LS diffs=DIFFS;
run;
```

where

- AVISITN is the visit as a categorical variable with visits up to and including Week 37
- TRTPG1 is the treatment groups, pooled active group, and placebo
- CHG is the change from baseline for all patients
- BASE is the baseline score for all patients
- LS and DIFFS are the respective output datasets

Actual and mean change from baseline in Total CAS will utilize the Efficacy Population with LOCF in study eye and either eye. Responder analyses will utilize Efficacy Population with LOCF in study eye and either eye; and Efficacy Population with ODO in study only. The MMRM analysis will utilize Efficacy Population with ODO in study eye only.

Figures for Total CAS responders over time in the study eye and separately in either eye as well as change from baseline over time in the study eye and separately in either eye for the Efficacy Population with LOCF will be presented. The CAS assessment will also be presented in a listing.

11.2.2 CLINICAL ASSESSMENT OF SPONTANEOUS ORBITAL PAIN, GAZE EVOKED PAIN, CONJUNCTIVAL REDNESS, CHEMOSIS, AND EYELID SWELLING

Spontaneous orbital pain assessment, gaze evoked pain assessment, conjunctival redness grade, chemosis grade, and eyelid swelling grade will be collected. These are being assessed independently from CAS as exploratory clinical severity endpoints. The assessments will be presented in listings.

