3.2.1 STUDY TREATMENTS

This study will include approximately 36 evaluable patients with TED in 4 treatment arms. Treatment-naïve patients will be randomized (in a 1:1:1 ratio) upon enrollment to LASN01 in either a high-dose (600 mg Q4W ×7-13 doses) or low-dose (300 mg Q4W ×7-13 doses) treatment arm or to placebo. [REDACTED]

[REDACTED] Treatment arms for the randomized and open-label patients are shown in Table 1. The protocol was amended as additional safety data became available to increase the duration of treatment with LASN01.

CONFIDENTIAL

The contents of this document are confidential to [REDACTED]
Unauthorized use, disclosure, or reproduction is strictly prohibited.

Table 1. Multiple Dose Study Design

Randomized Treatment Arm	Dose	Number of Doses	Number of Patients
1	Low-dose LASN01 (300 mg Q4W)	13	8
2	High-dose LASN01 (600 mg Q4W)	13	8
3	Placebo (Q4W)	13	8
Total Number of Patients			24

4. Sample Size

This study will enroll up to 36 evaluable patients with TED across four treatment arms. Approximately 24 patients will be randomized in a 1:1:1 ratio to receive LASN01 600 mg Q4W, LASN01 300 mg Q4W, or placebo.

Randomized Treatment Arms:

- The pooled primary analysis represents a 2:1 randomization of pooled LASN01 (300 mg and 600 mg arms) to placebo with about 24 patients.
- The placebo response rate is assumed to be ~15% (based on Teprotumumab FDA approval data from 2020).
- Assuming a pooled LASN01 response rate of 65% (an absolute treatment effect of 50% over placebo), a sample size of 8 patients per arm provides approximately 81% power at a 10% significance level using a one-sided Fisher's exact test.
- If the placebo response rate is 10%, the power increases to approximately 90% at the same significance level.
- Power calculations were performed using R Version 4.2.1 (R Core Team, 2022), employing simulation methods with 10,000 iterations implemented via the 'statmod' package (Giner, 2016).

CONFIDENTIAL

The contents of this document are confidential to [REDACTED]
Unauthorized use, disclosure, or reproduction is strictly prohibited.

5. Analysis Populations

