6.3 Data Analysis Conventions

Ora will perform all data analyses described in this SAP using [REDACTED]. Outputs will be provided in RTF for tables and figures, and in PDF for tables, listings, and figures (TLFs) in landscape orientation. Each formal TLF deliverable will include three combined PDF files, one for each of the output types.

Data will be summarized and listed separately. Continuous variables will be summarized using the number of patients (n), mean, standard deviation (SD), median, minimum, and maximum. Additionally, coefficient of variation (CV%), geometric mean and geometric CV% will be provided for PK concentrations and parameters (except for T_{max}). Values of 0 will be considered missing when calculating the geometric means. Categorical data will present counts and percentages within each category. Standard Error (SE) may be added to continuous efficacy outputs for Total CAS. Individual patient data listings will also be produced. For all other parameters except for PK concentrations and PK parameters, minima and maxima will retain the same precision as raw values; means and medians will have one additional decimal place; SDs will have two additional decimal places. For PK concentrations and parameters except n, all other descriptive statistics will be presented with the same number of significant digits as raw PK concentrations (3 significant figures). Percentages will be rounded to one decimal place (e.g., XX.X%). Differences between active treatment and placebo will be calculated as Active – Placebo, and change from baseline as Follow-up Visit – Baseline.

Unless otherwise specified, all statistical tests will be one-sided at a significance level of $\alpha=0.1$. Confidence intervals (CIs) for differences between treatment arms will be two-sided at 95% confidence unless stated otherwise. All p-values will be rounded to four decimal places; p-values less than 0.001 will be shown as "<0.001," and those greater than 0.9999 as ">0.999."

Summaries will be presented by treatment arm, including 300 mg, 600 mg, pooled treatment group (300 mg and 600 mg) for efficacy, placebo arm, [REDACTED] and, where appropriate, by visit and eye (study eye and either eye). Where possible, p-values will be displayed for comparisons of relevant active treatment groups to placebo; [REDACTED]. Listings will be presented by patient number, treatment arm, visit, time point, and parameter as applicable based on enrolled patients unless otherwise specified.

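### For Total CAS change, each dose is compared with placebo only by an unadjusted t-test, no main CAS result is named, and within-arm p-values invite misreading (minor)

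*SAP*

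**What the plan says.** Change in CAS against placebo, for each dose and for the pooled group, is a secondary endpoint in the protocol (sections 3 and 9.2.4) and in SAP section 2. SAP section 11.2 makes CAS the only secondary endpoint with summary tables, analysed with LOCF. SAP section 11.2.1 then plans five kinds of test:

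- **Responder (score 0 or 1):** one-sided Fisher tests, each dose and pooled v placebo, at each visit.
- **Within arm:** "one-sample t-tests will be provided to assess each individual arm and the pooled treatment arm change from baseline".
- **Two-sample t-test:** "p-values from a two-sample t-test will be provided to assess the individual treatment arm and the pooled active treatment differences as compared to placebo".
- **ANCOVA with baseline:** it "will be used to compare pooled active group to placebo for study eyes and separately for either eyes at each visit". The individual doses are not included.
- **MMRM:** pooled v placebo only. "The MMRM analysis will utilize Efficacy Population with ODO in study eye only".

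SAP section 6.3 sets the default: "all statistical tests will be one-sided at a significance level of" 0.1. Intervals for differences "will be two-sided at 95% confidence unless stated otherwise".

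SAP section 16 records that "An ANCOVA model has been added to existing mean and mean change from baseline Total CAS tables", again for the pooled group only. It describes the repeated-measures CAS model as a sensitivity analysis and the additions as exploratory. Section 6.4 states that there is no multiplicity adjustment.

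**The concern.** There are three linked weaknesses.

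1. **Dose contrasts.** These are the smallest comparisons in the trial, and the only ones on CAS change with no baseline adjustment. With 8 patients per arm, a chance imbalance in baseline CAS passes into the change score.
2. **Main result.** Section 11.1 fixes the test, visit and data handling for proptosis. Section 11.2.1 does not do this for CAS. The labels in section 16 leave open whether the t-test, the ANCOVA or the responder test is the CAS result, so a reader could take whichever looks better.
3. **Within-arm p-values.** Patients must enter with CAS of at least 4 (protocol section 5.1), so some fall is expected without any drug effect. A one-sample test cannot separate that fall from treatment. With 16 v 8 patients, the pooled group crosses the threshold more readily than placebo.

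At stake are the precision and the reading of a secondary endpoint that carries the supporting efficacy message.

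**Working it through.** **The plan's own figure.** SAP section 4 says that "a sample size of 8 patients per arm provides approximately 81% power at a 10% significance level" for the proptosis responder endpoint. Exact enumeration of the one-sided Fisher test, 16 v 8, gives 81.8% for 65% v 15% and 89.7% for 65% v 10%. The stated 81% and 90% reproduce. The documents give no power figure for CAS.

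**Inputs.** From the documents: 8 per arm, pooled 16 v 8, one-sided 0.10. Assumed, because the documents give none: baseline SD 1, follow-up SD 1.2, true effect 1.2 points, correlation r between baseline and follow-up from 0.3 upward.

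**Step 1: variance.** The change score has variance 1² + 1.2² − 2·r·1·1.2. ANCOVA leaves residual variance 1.2²·(1 − r²).

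| r | Change | ANCOVA | Ratio |
|---|---|---|---|
| 0.3 | 1.72 | 1.31 | 0.76 |
| 0.5 | 1.24 | 1.08 | 0.87 |
| 0.7 | 0.76 | 0.73 | 0.97 |

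**Step 2: single-dose t-test.** SE = SD·√(1/8 + 1/8) = SD/2. At r = 0.3 this is 1.311/2 = 0.656, so the noncentrality is 1.2/0.656 = 1.83 on 14 df and power is 69%. At r = 0.5 the SE is 0.557, the noncentrality 2.15 and power 79%. At r = 0.7 power is 92%.

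**Step 3: three-arm ANCOVA, same contrast (simulated).** Error df are 24 − 4 = 20. Power is about 76% at r = 0.3, 82 to 83% at 0.5 and 92% at 0.7. Part of the gain comes from estimating the residual variance across three arms; a two-arm ANCOVA gives about 75% and 80% at 0.3 and 0.5. If the two SDs are equal and the effect is 1 SD, t-test v three-arm ANCOVA is 64% v 76%, 74% v 82% and 89% v 91% at r = 0.3, 0.5 and 0.7, with no gain at 0.9. With no effect, both methods reject in about 10% of trials.

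**Step 4: disagreement on the pooled contrast.** With the 1.2-point effect, the t-test and the ANCOVA fall on opposite sides of 0.10 in about 12%, 6% and 2% of trials at r = 0.3, 0.5 and 0.7. In an illustrative model with integer scores (placebo mean about 3, effect 1.0 to 1.5 points, all assumed), the t-test, ANCOVA and responder test did not all agree in 38 to 42% of trials. Much of that reflects the lower power of the responder test.

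**Step 5: within-arm tests, no drug effect.** Noncentrality = fall/SD·√n, with n = 16 (15 df) for pooled LASN01 and n = 8 (7 df) for placebo. For a fall of 0.5 at r = 0.3 these are 0.5/1.311·4 = 1.53 and 0.5/1.311·2.83 = 1.08. The groups are independent, so the probabilities multiply.

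| Fall | r | Pooled p below 0.10 | Placebo p below 0.10 | Pooled only | Placebo only |
|---|---|---|---|---|---|
| 0.5 | 0.3 | 58% | 40% | 35% | 17% |
| 0.5 | 0.5 | 68% | 47% | 36% | 15% |
| 1.0 | 0.3 | 95% | 77% | 22% | 4% |
| 1.0 | 0.5 | 99% | 87% | 13% | 1% |

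The excess of 'pooled only' over 'placebo only' comes entirely from 16 v 8.

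**The case against.** The strongest reply is that this is a secondary endpoint in an openly signal-seeking study. The t-test holds its 10% error rate, the pooled contrast already has an ANCOVA, and the precision gain vanishes if baseline and follow-up are strongly correlated. All of that stands, and it is why the point is minor.

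Four stronger readings are tempting, and the documents do not support them:

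- **That each dose gets nothing but the t-test.** Each dose also has a Fisher responder test against placebo and a within-arm test. The gap is in the between-group analysis of continuous change.
- **That the CAS analyses are wholly unranked.** Section 16 calls the repeated-measures model a sensitivity analysis and the additions, ANCOVA among them, exploratory. On that reading the existing t-test ranks above the ANCOVA by implication, but no sentence says so, and the responder test is not placed.
- **That using several methods nearly doubles alpha.** With no effect, the two dose t-tests alone give at least one positive in about 17% of trials. Adding the pooled t-test leaves it at about 17%, and adding the pooled ANCOVA takes it to about 19 to 20%. Most of the inflation comes from testing two doses, which section 6.4 openly accepts.
- **That the SAP treats the one-sample tests as evidence against placebo.** It offers them only to assess change from baseline. The risk lies in how a reader contrasts the arms.

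A further objection has force: the sponsor's clinical team had been unmasked, so choosing a main analysis now comes after that event.

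**Conclusion.** The point holds as a modest matter of precision and clarity. Each dose's CAS change against placebo lacks a baseline adjustment that the plan already applies to the pooled group. Under the assumed SDs and effect, the cost is about 7 points of power at correlation 0.3, 3 to 4 points at 0.5, and none from 0.7. The SAP does not state which of the t-test, ANCOVA and responder test is the main CAS result, and the pooled t-test and ANCOVA could disagree in about 2 to 12% of trials over the same range. The within-arm p-values are easily misread: with no drug effect and an assumed fall of 0.5 to 1.0 point, 'pooled significant, placebo not' occurs in 13 to 36% of trials at correlations 0.3 to 0.5. No SD, effect, correlation or natural fall for CAS is given in the documents, so these are ranges under assumptions. No type I error fault and no effect on the primary analysis follows.

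**What to change.** In SAP section 11.2.1, with a matching line in section 16:

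1. Fit one ANCOVA of Total CAS change per visit with the three randomised arms and baseline CAS, using LOCF as in section 11.2 and ODO as the robustness check. Take both dose-v-placebo contrasts and the pooled contrast (equal weight on the two doses) from it, in place of the two-sample t-tests.
2. Before database lock, have the CRO statisticians, who section 16 says remain masked, name the Week 37 study-eye pooled contrast as the main CAS result. Label the MMRM and the responder tests supportive.
3. Replace the one-sample p-values with mean change and its interval.

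**Cost.** The work is SAP wording and minor programming, with no new data. The pooled contrast loses one degree of freedom (21 to 20), while the dose contrasts go from 14 to 20. Fewer p-values are reported. The change comes after the sponsor's clinical team was unmasked, and the study report should say so. It does not remove the inflation from testing two doses: the two dose contrasts and the pooled contrast together still give about 17% under no effect.
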